8.2.6 Response at 6 months

8.2.7 Response to a second cycle of Campath

8.3 Sample size

Because the efficacy of this treatment is almost completely unknown, we would like to reject the treatment as quickly as possible with a small number of subjects if the treatment is not effective. A response probability of 30% or less would warrant terminating the treatment on this patient population, and we hypothesize that the actual response probability using this treatment would reach 50% or more.

Let p be the probability of complete or partial response at 3 months. Our sample size is determined by testing the null hypothesis $H_0: p \leq 30\%$ versus the alternative $H_1: p \geq 50\%$ at 0.05 significance level and 0.80 of the power. We determine the sample size using the Two-Stage Minimax Design outlined in Table 1 of Simon (1989)⁵⁷. This design is selected because it requires a smaller total number of subjects ($n=39$) than the Simon's Two-Stage Optimal Design ($n=46$). At the first stage, 19 subjects will be accrued and the null hypothesis will be accepted (i.e., the treatment will be terminated) if 6 or less of the subjects respond to the treatment at 3 months. If 7 or more subjects respond to the treatment at 3 months at the first stage, then an additional 20 subjects will be accrued, bringing the total number of subjects to $n=39$. The null hypothesis of $p \leq 30\%$ will be accepted if the total number of complete and partial responders at 3 months is 16 or less.

8.4 Statistical Methods

The planned analyses will include descriptive statistics on the proportions of responses (i.e. % subjects with partial or complete response) and the time to response. The response probabilities will be estimated using the sample proportions and their inferences including confidence intervals and hypotheses testing will be evaluated using Binomial distributions.

The time to responses and the relapse-free survival will be analyzed using appropriate tools in survival analysis, such as cumulative incidence estimate and Cox regression type analysis for covariates, which takes into consideration both death without the event of interest as a complete risk and random censoring due to loss of follow-up. The Kaplan-Meier estimates and Cox regression will be used to evaluate the treatment effects on the overall survival. Graphical tools will be used to display the appropriate estimates (i.e. estimated proportions, the cumulative incidence curves, Kaplan-Meier curves) and their corresponding 95% confidence intervals.

Methods based on multiple regression, analysis of variance, and logistic regression will also be employed if deemed appropriate.

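### Do the 95% binomial intervals of Section 8.4 contradict the two-stage decision rule of Section 8.3 at 17 responders out of 39?

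*Combined protocol and SAP*

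**What the plan says.** Section 8.3 of the combined protocol and SAP fixes the two rates that matter: "A response probability of 30% or less would warrant terminating the treatment on this patient population", and the investigators expect that "the actual response probability using this treatment would reach 50% or more". It writes the null hypothesis as p at or below 30% and the alternative as p at or above 50%, to be tested "at 0.05 significance level and 0.80 of the power". The design is named: "We determine the sample size using the Two-Stage Minimax Design outlined in Table 1" of the cited design paper. Stage 1 has 19 subjects, and "the treatment will be terminated) if 6 or less of the subjects respond to the treatment at 3 months". Otherwise 20 more are accrued, and the null hypothesis "will be accepted if the total number of complete and partial responders at 3 months is 16 or less". So 17 or more of 39 rejects it.

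Section 8.4 covers estimation and reporting: "The response probabilities will be estimated using the sample proportions and their inferences including confidence intervals and hypotheses testing will be evaluated using Binomial" methods. The figure of 95% comes later, in the sentence on graphical display, which covers "estimated proportions, the cumulative incidence curves, Kaplan-Meier curves) and their corresponding 95% confidence intervals". Neither section uses the term one-sided or two-sided, and 8.4 does not mention the two-stage rule.

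**The concern.** A reader who takes the two sections together can reasonably ask whether they give one answer. The rule in 8.3 spends the whole 5% in the upper tail. A 95% interval, if two-sided as is usual, leaves 2.5% in each tail. At the smallest successful total the two part: 17/39 rejects 30%, but the 95% interval still contains 30%. A two-sided binomial p-value would also exceed 0.05 there. Section 8.4 names neither the side of its tests nor the two-stage rule.

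If the two were competing criteria, this would matter. A trial ending on the boundary could be reported as a success or a failure according to which line was read, and a choice made after seeing 17/39 would look driven by the data. There is a second worry behind it: fixed-sample binomial methods applied after a two-stage design might lose their stated coverage.

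**Working it through.** **Inputs.** All from Section 8.3: null rate 0.30; alternative 0.50; level 0.05; power 0.80; stage 1 of 19 subjects, stop at 6 or fewer; total 39, accept the null at 16 or fewer. From Section 8.4: binomial inference, 95% intervals.

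**1. Reproduce the design.** The probability of rejecting at true rate p is

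P(reject | p) = Σ (x₁ = 7 to 19) P(Bin(19, p) = x₁) × P(Bin(20, p) ≥ 17 − x₁).

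- p = 0.30: 0.0455, below 0.05.
- p = 0.50: 0.8036, above 0.80.

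A search over total sizes 36, 37 and 38 finds no design that meets both limits; at 39 it returns exactly the plan's rule. The stated figures are right.

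**2. Which side is the 0.05?** The null is p ≤ 30% and only a high count rejects, so the test is upper one-sided as written. The numbers confirm it. If 0.05 were two-sided, so that 0.025 applied to the upper tail, the same stage 1 stop would need 18 or more of 39. That has upper-tail error 0.0230 and power 0.7224, which misses the stated 0.80. Only the one-sided reading gives the plan's design.

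**3. The binomial test of Section 8.4 on the hypotheses of Section 8.3.** The one-sided fixed-sample p-value is P(Bin(39, 0.30) ≥ x):

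| Responders | Fixed-sample p | Two-stage p | Rule in 8.3 |
|---|---|---|---|
| 16/39 | 0.0944 | 0.0810 | accept |
| 17/39 | 0.04998 | 0.0455 | reject |
| 18/39 | 0.0242 | 0.0230 | reject |

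At 5% both p-values change sides between 16 and 17, where the rule does. The fixed-sample p-value cannot be the smaller of the two, because the two-stage calculation only removes outcomes that failed stage 1.

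A two-sided p-value at 17/39 is 0.1000 by doubling (2 × 0.04998) or 0.0793 by the minimum-likelihood method. Both test p = 30% against departures in either direction, which is not the hypothesis in 8.3.

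**4. The intervals.** The exact (Clopper–Pearson) lower limit is the α/2 quantile of Beta(x, 39 − x + 1). The 95% interval excludes 30% from below when the one-sided p-value is under 0.025; the test rejects when it is under 0.05. They can differ only at a total with a p-value between 0.025 and 0.05. The table in step 3 shows one such total, 17.

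| Responders | Exact 95% interval | Exact 90% lower limit |
|---|---|---|
| 16/39 | 25.6% to 57.9% | 27.7% |
| 17/39 | 27.8% to 60.4% | 30.001% |
| 18/39 | 30.1% to 62.8% | 32.3% |

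Other 95% methods also include 30% at 17/39 (Wilson 29.3% to 59.0%; two-stage 28.1% to 61.1%). So the difference comes from the tail level and not from ignoring the stages. At the matching level it disappears: the two-stage 90% interval at 17/39 is 30.3% to 58.6%.

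**5. Does the fixed-sample interval keep its coverage?** I took every possible outcome, with n = 19 for trials stopped at stage 1 and n = 39 otherwise, and computed the coverage of the exact 95% interval for p from 0.25 to 0.60 in steps of 0.001. It runs from 94.7% to 98.6% and is below 95% at 14 of 351 points.

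**6. How often the outcome arises.** The probability of ending at exactly 17/39 is 2.3% at p = 0.30, 10.1% at p = 0.40 and 8.1% at p = 0.50. As a share of rejecting trials that is 0.0812 / 0.8036 = 10.1% at p = 0.50 and 0.0225 / 0.0455, about 50%, at p = 0.30.

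**The case for a change.** The best case for the concern is this. The list in the 95% sentence of 8.4 includes estimated proportions, so the 95% does reach the response rate. Section 8.4 also promises hypothesis tests without giving a side, and an analyst who used software defaults could print 0.079 beside a result that 8.3 calls a rejection. The total concerned is the narrowest success, the result readers would examine most closely, and it makes up a sizeable share of rejections when the drug is truly marginal. Settling it would take a sentence or two.

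All of that is accurate, and the arithmetic behind it reproduces. What it shows is that the plan could be more explicit. It does not show two rival criteria. Section 8.3 gives a complete count rule, and nothing in 8.4 lets an interval override it. The two-sided p-value arises only if the written hypotheses are set aside. A two-sided 95% interval beside a one-sided 5% test is a common and valid pairing. At 17/39 its lower limit of 27.8% tells the reader, correctly, that the result is close to the boundary. A 90% interval is a reporting preference. A two-stage estimator or interval would not address the stated cause, since the two-stage 95% interval includes 30% as well.

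**Conclusion.** The concern does not hold. Followed as written, the plan gives a valid one-sided test (type I error 0.0455, power 0.8036), a binomial p-value that agrees with it at the boundary (0.04998 at 17/39), and an interval whose coverage under the two-stage design falls no lower than 94.7% for true rates between 25% and 60%. Test and 95% interval point different ways at one total only, because they use different tail levels, and the decision at that total is fixed by 8.3.

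This rests on three readings. The level in 8.3 is one-sided, which follows from its hypotheses and is confirmed by the power. The 95% interval is two-sided, which is usual but not stated; a one-sided 95% lower bound would remove even the apparent conflict. The interval is the exact binomial one, which 8.4 suggests but does not name; the coverage figure depends on that choice, while the result at 17/39 is the same for every 95% method tried. Stating the side in 8.3 and calling the 95% interval descriptive in 8.4 would be optional clarification.

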8.5 Stopping rules

The following two types of treatment related severe adverse events will be monitored and considered for early stopping for all or part of the study:

- Death considered to be definitely related to alemtuzumab (Campath-1H®)
- Any grade IV toxicity considered to be definitely related to alemtuzumab (Campath-1H®), i.e. opportunistic infection such as tissue-invasive CMV or *Pneumocystis jiroveci*, with exception of temporary cytopenias.

We will monitor the numbers of subjects who have developed one or more of the above treatment related severe adverse events (TRSAE). The study will be seriously considered for early stopping if the corresponding number of subjects who have developed one or more of the above TRSAE (Death or any grade IV toxicity considered definitely related to Campath) is over a pre-specified threshold value.

From our experience using this agent in other clinical settings, we anticipate the rate of developing at least one of the above TRSAE to be 10% or less within the first 6 months after first dose of study medication. Following Geller et al. (2003, “Design of Early Trials in Stem Cell Transplantation: A Hybrid Frequentist-Bayesian Approach”), our stopping rule is determined by a Bayesian approach.⁵⁸ The stopping boundary is reached if the Bayesian posterior probability that the true probability of developing one or more of the above TRSAE exceeds this benchmark rate of 10% is at least 90%. We take our prior distribution to be a beta distribution with the sum of the two beta parameters to be 5, i.e. the parameters of the beta prior distribution are 0.50 and 4.50. Since we have seen in the past that the first few subjects to be accrued are possibly sicker than the rest of the subjects in the sample, we will start safety monitoring when 3 or more subjects have developed TRSAE. The following table summarizes the threshold numbers for stopping an experiment:

Number of Subjects in the experiment	Stop if the number of subjects who have developed any of the TRSAE reaches:
≤ 10	3
≤ 17	4
≤ 24	5
≤ 32	6
≤ 39	7

We investigated the performance of the above stopping rule by a simulation study. In each simulation run, we generated a study with 39 independent Bernoulli trials, each had a probability p for having the above TRSAE and $q=1-p$ for not having such TRSAE and compared the TRSAE outcomes with the above stopping boundary to determine whether the study was stopped. We repeated the simulation 100,000 times and computed the proportion of stopped studies (i.e. “number of stopped studies”/100,000) which were stopped using the above stopping rule. The following table summarizes the proportions of stopped studies under a number of scenarios for p :

Prob of TRSAE = p	2%	5%	10%	15%	20%	25%
Proportion of Stopped Studies	0.1%	2.0%	17.5%	47.6%	75.4%	91.6%
Average Number of Subjects	38.96	38.5	35.2	28.8	21.8	16.0
Average Numbers of TRSAEs suffered by subjects	0.78	1.9	3.5	4.3	4.4	4.0

These results suggest that our stopping rule has a low probability of stopping a study when the proportion of the above TRSAE is below the benchmark value of 10%, and the probability of stopping a study is high when the true proportion of the above TRSAE exceeds this benchmark value. Based on these results, we believe that our Bayesian stopping rule has satisfactory statistical properties.

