9 DATA AND SAFETY MONITORING

9.1 Safety Monitoring

Principal investigator: Accrual, efficacy and safety data will be monitored by the PI.

NHLBI IRB: Accrual and safety data will be reviewed annually by the Institutional Review Board (IRB). Prior to implementation of this study, the protocol and the proposed consent form will be reviewed and approved by the properly constituted Institutional Review Board (IRB) operating according to the Title 45 CFR 46. This committee must approve all amendments to the protocol or informed consent, review all SAEs, and conduct continuing annual review so long as the protocol is open to accrual or follow up of subjects.

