9.2.3 Serious Adverse Events Management

Serious adverse events will be attributed as definitely (clearly related to the research), probably (likely related to the research), possibly (may be related to the research), unlikely (doubtfully related to the research) and unrelated (clear not related to the research).

Treatment related SAEs (TRSAEs) are those attributed as definitely, probably, or possibly. As detailed in section 8.5 stopping rules, only Death and any grade IV toxicities considered to be definitely related to alemtuzumab (Campath-1H®) will be monitored and considered for early stopping the study according to statistically determined criteria. [name], NIDDK will serve as the independent monitor who reviews the attribution of TRSAEs

Hospitalization (overnight admission) for routine supportive care (platelet or RBC transfusions) or admission from the NIH inpatient unit to the NIH ICU for routine monitoring will not be reported as a serious adverse event.

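### Section 8.5 contradicts itself on whether the toxicity boundary binds and on when it is crossed; its operating characteristics hold only if reaching the threshold ends accrual

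*Combined protocol and SAP*

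**What the plan says.** Section 8.5 opens by saying that definitely related deaths and grade IV toxicities "will be monitored and considered for early stopping for all or part of the study". It then gives the consequence of a crossing: "The study will be seriously considered for early stopping if the corresponding number of subjects" with at least one TRSAE is over a pre-specified value. Section 9.2.3 repeats that such events "will be monitored and considered for early stopping the study according to statistically determined criteria".

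The boundary table in Section 8.5 speaks differently. Its column heading is "Stop if the number of subjects who have developed any of the TRSAE reaches", followed by 3 (up to 10 subjects), 4 (up to 17), 5 (up to 24), 6 (up to 32) and 7 (up to 39).

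The simulation that follows ran 100,000 studies of 39 Bernoulli subjects and "compared the TRSAE outcomes with the above stopping boundary to determine whether the study was stopped". It tabulates the proportion stopped, the mean number of subjects and the mean number of TRSAEs, and the plan concludes that the rule performs satisfactorily.

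On oversight, Section 9.1 says "Accrual, efficacy and safety data will be monitored by the PI". The IRB reviews accrual and safety data annually and also reviews all SAEs. Section 9.2.3 gives an independent monitor the task of reviewing TRSAE attribution.

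**The concern.** Two things are left open: what happens at a crossing, and which count is a crossing. The prose makes the boundary a prompt for discussion once the count exceeds the threshold. The table and the simulation make it a stop once the count equals the threshold. These are different rules with different properties, and the plan reports properties for only one of them.

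The boundary marks the plan's own criterion: a posterior probability of at least 90% that the TRSAE rate exceeds 10%. If subjects may continue to enter after that, the reported sample sizes and event counts understate what could occur. The plan can write a binding rule when it means one: the futility rule in Section 8.3 equates accepting the null hypothesis with terminating the treatment. The safety prose has no equivalent.

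**Working it through.** **Inputs (all Section 8.5).** Prior Beta(0.50, 4.50); benchmark rate 10%; posterior criterion 90%; monitoring from 3 events; maximum 39 subjects; the boundary table and the simulation table.

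**Step 1: the boundary.** With k events in n subjects the posterior is Beta(0.5 + k, 4.5 + n − k). The smallest k of at least 3 with P(rate > 0.10) ≥ 0.90 is 3 up to n = 10, 4 up to 17, 5 up to 24, 6 up to 32 and 7 up to 39. This is the plan's table exactly. The posterior criterion is therefore met when the count *reaches* the tabulated value, not when it is over it.

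**Step 2: the operating characteristics.** Let f(n, k) be the probability of k events after n subjects with no earlier crossing. Then f(n, k) = f(n−1, k)(1 − p) + f(n−1, k−1)p, and any mass at or above the threshold for n is removed as stopped.

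| True TRSAE rate | 2% | 5% | 10% | 15% | 20% | 25% |
|---|---|---|---|---|---|---|
| Stopped, plan (%) | 0.1 | 2.0 | 17.5 | 47.6 | 75.4 | 91.6 |
| Stopped, exact, *reaches*, crossing at subject 39 not counted (%) | 0.1 | 2.0 | 17.5 | 47.6 | 75.5 | 91.5 |
| Stopped, exact, *reaches*, crossing at subject 39 counted (%) | 0.1 | 2.1 | 18.0 | 48.8 | 76.9 | 92.3 |
| Stopped, exact, *over*, crossing at subject 39 counted (%) | 0.0 | 0.3 | 6.6 | 28.7 | 59.5 | 83.1 |
| Mean subjects, plan | 38.96 | 38.5 | 35.2 | 28.8 | 21.8 | 16.0 |
| Mean subjects, exact, *reaches* | 38.97 | 38.5 | 35.2 | 28.8 | 21.7 | 16.1 |
| Mean subjects, exact, *over* | 39.0 | 38.9 | 37.9 | 34.3 | 28.6 | 22.4 |
| Mean TRSAEs, plan | 0.78 | 1.9 | 3.5 | 4.3 | 4.4 | 4.0 |
| Mean TRSAEs, exact, *reaches* | 0.78 | 1.92 | 3.52 | 4.32 | 4.35 | 4.02 |
| Mean TRSAEs, exact, *over* | 0.78 | 1.95 | 3.79 | 5.15 | 5.71 | 5.61 |

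The plan's figures are reproduced under *reaches* with every crossing ending accrual. Whether a crossing at subject 39 counts as a stop does not alter the means, since 39 subjects are enrolled either way.

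**Step 3: why the means need a binding rule.** Mean events equal p times mean subjects: 0.20 × 21.8 = 4.36 and 0.25 × 16.0 = 4.0. The low event counts come entirely from accrual ending early.

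**Step 4: if the boundary is advisory.** Let c be the chance that a crossing actually stops the study, and let a study not stopped run to 39. The documents give no value for c, so the whole range from 0 to 1 is an assumption.

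- Proportion stopped = c × (binding proportion)
- Mean subjects = c × (binding mean) + (1 − c) × 39
- Mean TRSAEs = c × (binding mean) + (1 − c) × 39p

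| | 20%: stopped / subjects / TRSAEs | 25%: stopped / subjects / TRSAEs |
|---|---|---|
| c = 1 | 76.9% / 21.7 / 4.35 | 92.3% / 16.1 / 4.02 |
| c = 0.5 | 38.4% / 30.4 / 6.07 | 46.1% / 27.5 / 6.88 |
| c = 0 | 0% / 39 / 7.8 | 0% / 39 / 9.75 |

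The last row is simply 39 × 0.20 and 39 × 0.25.

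**The case against.** An advisory safety boundary is legitimate, and investigators often want discretion. That stands. But the stated percentages are then probabilities of triggering a review, and the mean sample sizes and event counts need a qualification they do not have.

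A reader might infer that a crossing leads to consideration and nothing more. The documents do not support this, because the table is headed as an instruction to stop and the text calls it a stopping rule. What can be shown is a contradiction, not a plainly advisory rule.

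A reader might also infer that a crossing need not reach the IRB before its annual review, or that the principal investigator alone decides. Neither is supported. Section 9.2.4.2 asks that an excess frequency or severity of expected events be reported as an unanticipated problem to the IRB and Clinical Director within the usual timeframes. Section 9.2.4.1 sends SAEs to the IRB chair and Clinical Director within 14 days, and Section 9.1 has the IRB review all SAEs. Section 9.1 says that the investigator monitors, not that the investigator is the sole decision-maker. These routes can bring the matter to the IRB early. What remains is that none of them mentions the boundary or says what happens to accrual. The opening of Section 9.2.4 was not available to me, so I make no claim about its content.

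Finally, one might project several extra subjects from a half-year wait for annual review. The plan gives no accrual rate, and the 14-day SAE route makes such a wait a slow case, so I do not rely on it.

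**Conclusion.** The contradiction is real and should be corrected. The operating characteristics in Section 8.5 are arithmetically sound, but they belong to a rule under which reaching the threshold ends accrual. The prose of Sections 8.5 and 9.2.3 does not impose that rule.

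The trigger wording alone lowers the chance of stopping at a 20% TRSAE rate from 76.9% to 59.5%, and at 25% from 92.3% to 83.1%, with a crossing at subject 39 counted in both. If crossings are advisory, mean TRSAE subjects lie between the stated 4.4 and 7.8 at 20%, and between 4.0 and 9.75 at 25%, depending on an adherence that the plan does not specify. The upper figures are bounds: they assume that no crossing is ever acted on, and they ignore the futility stop at 19 subjects in Section 8.3. They are not a forecast.

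The finding rests on the conflict within Section 8.5 and its repetition in Section 9.2.3. It does not rest on any supposed absence of reporting to the IRB.

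**What to change.** Reconcile the prose, table heading and simulation in Section 8.5 with Section 9.2.3.

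- Use one trigger word throughout. The posterior criterion and the simulation both match *reaches*; if *over* is intended, the table of operating characteristics must be recomputed.
- State whether a crossing is binding, what happens to new enrolment while it is reviewed, and who decides. The existing principal investigator, IRB and Clinical Director are enough for this.
- If the boundary stays advisory, relabel the percentages as probabilities of triggering a review. Qualify the mean sample sizes, the event counts and the conclusion about the rule's performance.

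Which stopping action to adopt is for the sponsor and IRB. The change takes a few sentences and no new committee. Its cost is either less favourable stated figures or, if the sponsor chooses a pause, an occasional short interruption of enrolment. By the plan's own table a crossing occurs in about 2% of studies at a true rate of 5% and in 17.5% at 10%.

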5.2 Re-treatment (per PI discretion)

Subjects who do not respond to initial cycle or relapse following initial treatment may be retreated at the discretion of principal investigator with an additional cycle of Campath 10 mg/dose IV for 10 days anytime after the 3 month (primary assessment) time point.

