6.2 On study drug monitoring: (cycle 1 and if applicable cycle 2)

On treatment monitoring will consist of:

- CBC with differential (daily)
- Chem 20 panel (every other day)
- Reticulocyte count (weekly +/- 3 days)
- Vital signs (daily)
- ECHO and 24 hour Holter monitor after last dose alemtuzumab (Campath®)
- Serum troponin at day 5 and after the last dose of alemtuzumab (Campath®)
- EBV and CMV PCR in the blood (weekly +/- 3 days)
- Chest x-ray, CT scans or appropriate imaging studies (only as medically indicated)

6.3 Post treatment monitoring discharge home through 3 months: After completing treatment, subjects will be followed by their home physician or at the Clinical Center and have blood work done as detailed below. Progress notes and laboratory results from home physicians will be faxed to [name], R.N., Research Nurse. Subjects must be evaluated at the Clinical Center at the 3 month (± 7 days) time point

- Interim Assessment
- Complete blood counts with differential (weekly +/- 3 days)
- DAT (NIH) or Coombs test (monthly +/- 2 weeks)
- Chem 20 panel (weekly +/- 3 days) (Home MDs: electrolytes, transaminases, urea nitrogen (BUN), serum creatinine, total bilirubin)
- EBV and CMV PCR in the blood (weekly +/- 3 days) for the first month, then every other week +/- 3 days) in the second month, and then monthly (+/- 2 weeks)
- Reticulocyte count (at 3 months only +/- 2 wks, home MDs only if available)
- ECHO (at 3 months only +/- 2 wks)
- Serum troponin (at 3 months only +/- 2 wks)

- Thyroid function tests (at 3 months only +/- 2 wks)
- Peripheral blood flow cytometry (at 3 months only +/- 2 wks)

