9.2.2 Adverse Events Management

. The AEs will be attributed (unrelated, unlikely, possibly, probably or definitely) to study medication and/or disease. AEs will be graded by severity utilizing CTC version 2.0. A copy of the criteria can be down-loaded from the CTEP home page at <http://ctep.cancer.gov/reporting/ctc.html>.

Abnormal laboratory findings used to evaluate the safety of this protocol regimen will be collected to include any change from laboratory assessments done prior to first dose of study medication that result in a progression to a grade 3 or 4 laboratory toxicity. The laboratory toxicities will be attributed (unrelated, unlikely, possibly, probably or definitely) to study medication and/or disease. They will be graded by severity utilizing CTC version 2.0.

Length of Adverse Event reporting: Adverse event collection will continue for 6 months after the last dose of Campath after which the events will be recorded in the medical record but not abstracted to toxicity tables. Serious adverse event reporting will continue as long as the subject remains on study.

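### Does the toxicity stopping rule in section 8.5 need a stated counting window and a rule for second-cycle events?

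*Combined protocol and SAP*

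**What the plan says.** Section 8.5 monitors deaths and grade IV toxicities judged definitely related to alemtuzumab, leaving out temporary cytopenias. The benchmark has a clock: the anticipated rate is "10% or less within the first 6 months after first dose of study medication". The boundary is reached when the posterior probability that the true rate exceeds that benchmark is at least 90%, under a Beta(0.5, 4.5) prior and with at least three affected subjects. The count itself is described without a clock: "We will monitor the numbers of subjects who have developed one or more of the above treatment related severe adverse events (TRSAE". The threshold table runs from 3 affected subjects (up to 10 treated) to 7 (up to 39). On crossing, "The study will be seriously considered for early stopping". The operating characteristics come from a simulation: "In each simulation run, we generated a study with 39 independent Bernoulli trials", one outcome per subject.

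Section 5.2 permits a second full course, at the principal investigator's discretion, "anytime after the 3 month (primary assessment) time point". Section 6.2 applies on-drug monitoring to both cycles, and 8.2.7 lists "Response to a second cycle of Campath" as a secondary endpoint. On data collection, section 9.2.2 states: "Adverse event collection will continue for 6 months after the last dose of Campath". It keeps serious adverse event reporting open for as long as the subject is on study. Section 9.2.3 refers back to 8.5 and adds neither a window nor a rule on cycles.

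**The concern.** A stopping probability can be read against a benchmark only if both refer to the same period of risk. Here the benchmark is a 6-month rate from first dose, while the count, read literally, is of subjects who have ever had an event. After a single 10-day course the two nearly coincide. After a second course they separate.

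Two readers could therefore apply the plan's only numerical toxicity boundary differently. If every event counts, second-cycle toxicity is added to a count judged against a first-6-month rate, and a trial exactly at the benchmark crosses more often than the table says. If the count is cut at 6 months from first dose, toxicity from a later second cycle meets no numerical boundary. A choice between these made after events had occurred would be open to the charge of being post hoc.

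**Working it through.** **1. The boundary.** Inputs from 8.5: Beta(0.5, 4.5) prior, benchmark 10%, posterior cut-off 0.90, minimum 3 events. For k affected subjects out of n, the posterior is Beta(0.5 + k, 4.5 + n − k), and the boundary is the smallest k ≥ 3 with P(rate > 0.10) ≥ 0.90.

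| k / n | P(rate > 0.10) | same k, one more subject |
|---|---|---|
| 3 / 10 | 0.913 | 0.895 |
| 4 / 17 | 0.908 | 0.894 |
| 5 / 24 | 0.910 | 0.897 |
| 6 / 32 | 0.903 | 0.891 |
| 7 / 39 | 0.909 | 0.899 |

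Every row of the threshold table reproduces.

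**2. The simulation table.** An exact recursion over 39 sequential subjects, stopping whenever the count reaches the boundary, gives:

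| p | 2% | 5% | 10% | 15% | 20% | 25% |
|---|---|---|---|---|---|---|
| Exact | 0.1% | 2.1% | 18.0% | 48.8% | 76.9% | 92.3% |
| Stated | 0.1% | 2.0% | 17.5% | 47.6% | 75.4% | 91.6% |

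If a crossing at the last subject is not counted as a stop, the exact values at 10% and 15% are 17.5% and 47.6%, as tabled. The table is right for whatever per-subject probability p it is given. Only the period that p covers is in question.

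**3. If all events count.** Let p1 be the 6-month risk, r the share retreated after month 6, and p2 the second-cycle risk, taken as independent. Then p = 1 − (1 − p1)(1 − r·p2). The documents give neither r nor p2; the values below are assumptions. With p1 = 10%:

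| r | p2 | p | crossing |
|---|---|---|---|
| 0.25 | 5% | 1 − 0.9 × 0.9875 = 11.1% | 24.1% |
| 0.25 | 10% | 1 − 0.9 × 0.975 = 12.25% | 31.0% |
| 0.50 | 5% | 1 − 0.9 × 0.975 = 12.25% | 31.0% |
| 0.50 | 10% | 1 − 0.9 × 0.95 = 14.5% | 45.6% |

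The comparison is 18.0% with no second-cycle events. A simulation that also models accrual and event timing, with second cycles starting in months 6 to 18, gives 19–30% (r = 0.25) and 24–43% (r = 0.5), against 15–18% without retreatment.

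**4. Below the benchmark.** With r = 0.5 and the same risk in each course:

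| risk per course | p | crossing |
|---|---|---|
| 7.5% | 10.97% | 23.2% |
| 5% | 7.4% | 7.2% |
| 2% | 2.98% | 0.4% |

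For comparison, one course alone gives 2.1% at 5% risk and 0.1% at 2% risk.

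**5. If the count is cut at month 6.** Assume second-cycle events fall evenly over the 2 months after that course starts (section 2.3.3.1 places most infections within 8 weeks). Starts before month 4 put all their events inside the window; starts in months 4 to 6 put half inside on average. That is 1 + 2 × 0.5 = 2 months' worth of starts.

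| starts spread over | inside the count | outside |
|---|---|---|
| months 3–6 | 2/3 = 67% | 33% |
| months 3–12 | 2/9 = 22% | 78% |
| months 3–24 | 2/21 = 9.5% | 90% |

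**6. What a heavier remedy would cost.** Keep the prior sum at 5, centre the prior on a two-course benchmark, and re-derive the boundary:

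| benchmark | boundary at n = 10 | boundary at n = 39 | crossing at true 20% |
|---|---|---|---|
| 10% (as planned) | 3 | 7 | 77% |
| 12.25% | 4 | 8 | 64% |
| 14.5% | 4 | 10 | 49% |

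The loss falls on all subjects, including those who had only one course. The alternative is a separate second-cycle boundary. Applying the planned rule to 10 retreated subjects would detect a true 20% rate 32% of the time.

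**The case for a change.** The case for acting is that this is the only numerical safety boundary, that 8.5 never mentions a second cycle which other sections plan for, and that the wording supports two counts. Section 9.2.2 adds two further clocks, and 9.2.3 does not choose among them. Carrying the 6-month window over by inference also treats second cycles unevenly: an event after an early retreatment may count, while one after a late retreatment does not. Settling this in advance would take one paragraph and no new data.

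The omission stands, and a clarifying sentence would do no harm. The rest weakens on inspection. The stopping criterion refers back to the benchmark just defined, so the 6-month rate is the natural meaning of p throughout. The clocks in 9.2.2 govern data collection, which has to last at least as long as the count it feeds. They supply the data for either reading and contradict neither. The larger crossing figures need cycle 1 toxicity at the very top of the anticipated range and retreatment after month 6, whereas 5.2 opens retreatment as soon as the month-3 assessment is done. Section 2.5 reports no serious treatment-related SAEs to that point, though without the number treated.

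**Conclusion.** No change follows. The text leaves a real gap in detail, but no figure in it is wrong, and those running the trial can fill it sensibly. The data allow the count to be shown both ways. Where the two counts fall on the same side of the boundary, the question does not arise. Where they differ, the literal count includes every event and so brings the review forward, and that review is a judgement about all or part of the study.

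Under the narrower count, second-cycle toxicity still meets on-drug monitoring (6.2), IRB review of all SAEs (9.1), independent review of attribution (9.2.3), and reporting limits of 14 days for SAEs and 7 days for deaths (9.2.4.1).

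The size is uncertain. Crossing rises from 18% to between 24% and 46% at a 10% first-course risk, and only to 7% or 0.4% at 5% or 2% per course with half retreated. All of this rests on assumed retreatment shares, risks, timing and independence. Re-deriving the boundary or adding a second one is a debatable trade, because detection of a true 20% rate would fall to 64% or 49%, or would rest on very few retreated subjects.
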